Sample size and power calculation We estimated that a sample size of 1200 across ten sites would be needed to test efficacy of UMC versus ECC for the primary outcome. This was based on the following assumptions: a clinically meaningful 35% reduction in NICU admissions (16.25% for UCM versus 25% for ECC), a two-sided type I error alpha = 0.05, 85% power, 0.02 rho (within cluster within period correlation), 0.02 eta (within cluster between period correlation), and a correction factor (4 x cluster size) for the small number of clusters(51).

For the longer-term neurodevelopment outcome scores, we estimated that a sample size of 1200 across ten sites, with an assumed two-sided type I error alpha = 0.05, 0.02 rho, 0.02 eta, a correction factor (4 x cluster size) for the small number of clusters, and Cohen's d = 0.25, power ranges from 79% to 87% when assuming a range in lost to follow-up from 20% to 10%. The original sample size for this trial was 1000. However, at the first DSMB meeting in May 2019 only four sites had begun enrollment and enrollment was nearing completion of the crossover point (nearly 2/3 complete in the first arm), and two sites were unable to obtain IRB approval. Therefore in conjunction with the DSMB, the decision was made to reassess the sample size calculation for ten sites.

Feasibility Based on the numbers of newborns at each of ten sites, we expect a total of approximately 1500 newborns with a 1-minute Apgar of ≤ 3 per year. Estimating conservatively that at least 50% will be classified as non-vigorous, a 2-year period of recruitment would be required. The ten sites agree to recruit and each one has provided an estimated number 35-41+6 weeks infants delivered per year.

Statistical Approaches for Testing Hypotheses

All statistical analyses will be based upon the total cohort of patients randomized into the trial. Patients will be included in the treatment group to which they were randomly assigned. We will use the intent-to-treat analysis to determine treatment difference between the UCM and ECC groups.

Descriptive statistics (counts and proportions for categorical variables and means and standard deviations or medians and interquartile ranges for continuous outcomes) will be used to compare baseline demographic, physiologic and clinical

outcomes between the two treatment groups. All statistical tests are two-sided with alpha = 0.05.

Analysis of Primary Outcome (NICU Admission)

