Secondary outcomes (use of therapeutic hypothermia, use of volume expanders, hemoglobin, bilirubin, death, and neurodevelopmental follow up scores) will be analyzed using similar multivariable procedures accounting for the study design as for the primary outcome to test treatment effects. Analyses will estimate relative risks and 95% confidence intervals for binary outcomes and means or mean differences and 95% confidence intervals for continuous outcomes. Secondary outcomes will be evaluated for missing data and those with and without missing data will be compared. Multiple imputation analysis will be conducted as warranted. Analyses will also evaluate death as a competing risk. No adjustment for multiple comparisons of secondary outcomes is planned.

Exploratory Analyses

Several outcomes are identified as exploratory (level of HIE, blood pressure, length of hospitalization, resuscitation interventions, and placental pathology). These analyses will focus on descriptive statistics rather than hypothesis testing. Likewise any evaluations of subgroup differences by treatment group (other than race/ethnicity as mentioned previously) will be explored in secondary analyses for descriptive purposes and solely for purposes of generating hypotheses for future studies.

Follow up Study- While all secondary and exploratory outcomes that occur during the delivery hospitalization will be presented in the primary paper, all subjects will continue to be followed until 24 months of age to determine their long-term outcome. The sample size is powered to detect differences in their Ages and Stages Composite and MCHAT scores.

Substudies for cerebral oxygenation and echocardiography will be reported as separate projects on clinical trials.gov and analyzed independently.

VI. Recruitment

Eligibility criteria

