Screening ID, Month/Year of birth, gestational age, SGA, time of cord clamping, Breathing or crying prior to cord clamping, birth assessment of tone, number of times cord milked, location of infant when milked (i.e. mothers abdomen, below level of introitus) birth weight, gender, APGARS at 1 and 5 minutes, resuscitation procedures (CPAP, PPV, intubation, chest

compressions, epinephrine, max FiO₂), NIRS data, disposition (NICU admission, or stable and staying with parent), pregnancy and delivery risk factors (diabetes, suspected or confirmed Triple I, hypertension, rupture of membranes).

After Informed Consent we will collect the following full data set:

Maternal data from infant's chart: Age, Race/Ethnicity, Level of Education, Mode of Delivery, Anesthesia (general, Spinal Epidural), Medications, Placental Weight. All maternal data will be collected from the infant's chart; the mother's chart will not be accessed for study purposes.

Infant data: Includes all data collected under waiver, plus Race/Ethnicity, Multiple gestation, length (cm), head circumference (cm), Hemoglobin between 12-48 hrs, Venous and/or arterial cord pH (if available), cardiac US, Peak total serum bilirubin (mg/dL) or Transcutaneous Bilirubin level, Polycythemia in the first week of life (Hct >65%), Duration of phototherapy days, Use of cardiac inotropes (dopamine, dobutamine, epinephrine), Early onset sepsis (positive blood or CSF culture at < 72 HOL), Duration of intubated and mechanical ventilation (days), Need for blood transfusion (DOL of 1st transfusion and total number), Length of hospitalization (total days), ASQ3, MCHAT, MRI white matter injury, HIE: mild, moderate, severe (initial screen completed at 1-6 hours of life), HIE: mild, moderate, severe (highest stage before discharge), Therapeutic Hypothermia, Placental pathology, PPHN.

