Appendix 1 Data Collected**DATA COLLECTED ABOUT INFANTS
AND MOTHERS****Maternal data from infant's chart:**

1. Age
2. Race/Ethnicity
3. Diabetes (gestational, Type 1 or 2) (yes/no)
4. Suspected or confirmed Triple I, chorioamnionitis (yes/no)
5. Hypertension (yes/no)
6. Rupture of Membranes (hours)
7. Mode of Delivery
8. Type of Anesthesia
9. Maternal medications (i.e. magnesium, fentanyl)
10. Placental Weight
11. Level of education
12. COVID-19 confirmed positive

**Data collected from all eligible infants
under waiver:**

13. Screening ID
14. Month/Year of birth
15. Birth assessment of tone
16. ECC or # times Milked
17. Timing of cord clamping
18. Breathing/Crying before cord clamped
19. 1 and 5 min Apgar
20. Resuscitation interventions (cpap, ppv, intubation, compressions, epinephrine, max Fio2)
21. NIRS, HR, SpO2 in del room
22. Gestational Age
23. Birth Weight
24. Gender
25. Disposition(NICU, Death or Dyad care)
26. Infant/delivery risk factors
27. NICU admission Dx
28. Reason Peds called to delivery
29. Multiple Gestation
30. COVID-19 confirmed positive

Infant data collected after consent:

31. Length, FOC (cm)

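### Maternal education is collected but not prespecified in any analysis of the parent-reported 24-month outcomes, so a modest precision gain is left to chance and covariate choice is left to the data

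*Combined protocol and SAP*

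**What the plan says.** **Collection.** Section IX (Data Collection) lists the maternal items taken after consent: "Age, Race/Ethnicity, Level of Education, Mode of Delivery, Anesthesia (general, Spinal Epidural), Medications, Placental Weight". Appendix 1 lists "Level of education" again among the maternal data. The source is restricted: "All maternal data will be collected from the infant's chart; the mother's chart will not be accessed for study purposes".

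**Outcome.** Hypothesis H4 concerns the ASQ-3 and M-CHAT-R at 24 months. The follow-up strategy in Section IV makes both of them parent-completed instruments.

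**Analysis.** Section V (Analysis of Secondary Outcomes) says that the secondary outcomes, including the follow-up scores, "will be analyzed using similar multivariable procedures accounting for the study design as for the primary outcome to test treatment effects". The primary analysis text contains one covariate rule: adjust if the arms turn out to differ on a pre-treatment factor known to affect the outcome. The secondary text compares infants with and without missing data and allows multiple imputation where it is judged to be needed. No covariate, imputation variable or criterion for a difference between arms is named.

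**Power.** For the follow-up scores, Section V takes 1200 infants in ten sites, a two-sided alpha of 0.05 and both correlations at 0.02. It reduces the sample for the small number of clusters by four times the cluster size. For a standardised difference of 0.25 it then reports that "power ranges from 79% to 87% when assuming a range in lost to follow-up from 20% to 10" per cent. No covariate is mentioned.

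**The concern.** A developmental score reported by a parent, and whether that parent returns the form over two years, can both reasonably be expected to depend on the parent's education. Education is fixed before treatment and is already on the data collection list, yet nothing commits the trial to using it.

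Two things follow. First, a rule triggered by observed imbalance gives no precision gain when the arms look balanced, although a prognostic covariate improves precision then too. Second, which covariates enter, and what counts as a difference, would be decided after the data are seen, in an unblinded trial.

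The setting adds some weight. There are only ten clusters, and consent to follow-up is sought after the allocated treatment has been given. The followed infants in the two arms may therefore differ in family background in ways that randomisation does not control.

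**Working it through.** **1. Inputs from Section V.** N = 1200, ten sites, two-sided alpha 0.05, rho = eta = 0.02, d = 0.25, loss of 20% or 10%, correction of 4 x cluster size. From these:
- infants per site: 1200/10 = 120, so the correction is 4 x 120 = 480;
- infants per site-period: m = 60;
- design effect: 1 + (m - 1) rho - m eta = 1 + 59 x 0.02 - 60 x 0.02 = 0.98.

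**2. Reproducing the plan's power.** Effective n per arm = [1200 x (1 - loss) - 480] / (2 x 0.98), and power = Phi(d x sqrt(n/2) - 1.96).
- 20% loss: n = (960 - 480)/1.96 = 244.9; 0.25 x sqrt(122.4) = 2.766; power 79.0%.
- 10% loss: n = (1080 - 480)/1.96 = 306.1; 0.25 x sqrt(153.1) = 3.093; power 87.1%.

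Both match. Other readings of the correction do not: no deduction gives 97.5% and 98.6%, and a deduction that shrinks with loss (384 and 432) gives 85.8% and 89.5%. The stated power is therefore an unadjusted calculation with a fixed deduction of 480.

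**3. Power with adjustment.** Replace d by d / sqrt(1 - R2), where R2 is the share of ASQ-3 variance explained jointly by education, infant sex and gestational age beyond the design terms. The documents give no R2, so a range is shown. The equivalent number of extra followed infants is (followed N - 480) x [1/(1 - R2) - 1].

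| Assumed R2 | Power, 20% loss | Extra infants | Power, 10% loss | Extra infants |
|---|---|---|---|---|
| 0 | 79.0% | 0 | 87.1% | 0 |
| 0.01 | 79.4% | 5 | 87.5% | 6 |
| 0.02 | 79.8% | 10 | 87.8% | 12 |
| 0.05 | 81.0% | 25 | 88.7% | 32 |
| 0.10 | 83.0% | 53 | 90.3% | 67 |
| 0.15 | 85.1% | 85 | 91.8% | 106 |

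For example, at 20% loss and R2 = 0.15, 480 x (1/0.85 - 1) = 85.

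**4. Dropout illustration (all inputs assumed).** Lower-education families are half the cohort and score 0.3 or 0.5 SD lower. The other families are retained at 90% in both arms. Lower-education families are retained at 80% in one arm and at 70% or 60% in the other.
- Lower-education share of completers at 80% retention: 0.8/(0.8 + 0.9) = 47.1%.
- At 70%: 0.7/1.6 = 43.75%. At 60%: 0.6/1.5 = 40.0%.
- Smallest shift in the unadjusted difference: 0.3 x (0.471 - 0.4375) = 0.010 SD.
- Largest shift: 0.5 x (0.471 - 0.400) = 0.035 SD, or 0.035/0.25 = 14% of the target effect.
- If retention by education is the same in both arms, the shift is zero.

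**The case against.** **The plan does not exclude education.** A reader might infer that it enters no planned analysis. The documents do not support that. Baseline demographics are compared by arm, adjustment follows if the arms differ on a known risk factor, completers are compared with non-completers, and imputation is possible. Education could enter by any of these routes. What stands is that none of them names it. The baseline and completer comparisons adjust nothing, and the other two routes are conditional.

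**The size is uncertain and not due to education alone.** The 5-15% is assumed and covers three variables. Comparison within sites already removes differences between sites, so only variation within sites counts. If the joint R2 is 1-2%, little is gained. The M-CHAT-R risk category is binary and would be analysed as a relative risk; no gain was computed for it, and it may be smaller. All of this stands.

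**The gain is easily overstated.** Scaling all followed infants by 1/(1 - R2) suggests about 50 (960/0.95 - 960) to 190 (1080/0.85 - 1080) extra infants. That ignores the fixed deduction of 480, and the table gives the figures consistent with the plan's own formula.

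**Dropout bias is hypothetical.** Nothing in the documents suggests that education-related loss would differ by arm. Repeated contact, online, paper or assisted telephone completion and a 90% follow-up goal all work against it. This stands, but the precision argument does not depend on dropout.

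**The fix is not free.** Because education comes only from the infant's chart, some values may be missing.

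**Conclusion.** The point holds as a modest but worthwhile improvement to the analysis of H4. Always adjusting for prognostic baseline variables that are already collected is better than adjusting only when an undefined imbalance appears. It secures whatever precision is available and removes a choice made after seeing the data.

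Under an assumed joint R2 of 5-15%, ASQ-3 power gains about 2.0 to 6.1 points at 20% loss and 1.6 to 4.7 points at 10% loss. At R2 = 0.05, power at 20% loss passes 80%. At R2 of 1-2%, the gain is under one point.

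A reader might infer that the stated 79-87% power is wrong, or that an analysis without education would be invalid. Neither follows: the power reproduces and simply assumes no covariate, and the unadjusted comparison remains a legitimate analysis. Nor can adjustment be presented as a general cure for attrition. It removes bias only where loss related to education differs by arm, and it cannot help with families who never consent. The primary outcome is not affected.

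**What to change.** 1. In Section V (Analysis of Secondary Outcomes), state that the 24-month ASQ-3 model always includes maternal education in fixed categories, infant sex and gestational age, together with the design terms, whatever the observed balance. Specify the same for the M-CHAT-R model, noting that the gain there may be smaller.
2. Name the same variables in any imputation model for these outcomes.
3. In Section IX and the follow-up procedures, have the coordinator ask for maternal education at consent, or at the 3-month call, if the infant's chart lacks it.
4. Fix in advance a rule for infants whose maternal education is still missing.

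The cost is a short addition to the analysis text and one question in a contact that is already planned. Some covariate values will remain missing, particularly for families lost before the 3-month call, and the rule in item 4 has to cover them. The stated power can stay as the unadjusted figure.

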Appendix 1 Data Collected**DATA COLLECTED ABOUT INFANTS
AND MOTHERS****Maternal data from infant's chart:**

1. Age
2. Race/Ethnicity
3. Diabetes (gestational, Type 1 or 2) (yes/no)
4. Suspected or confirmed Triple I, chorioamnionitis (yes/no)
5. Hypertension (yes/no)
6. Rupture of Membranes (hours)
7. Mode of Delivery
8. Type of Anesthesia
9. Maternal medications (i.e. magnesium, fentanyl)
10. Placental Weight
11. Level of education
12. COVID-19 confirmed positive

**Data collected from all eligible infants
under waiver:**

13. Screening ID
14. Month/Year of birth
15. Birth assessment of tone
16. ECC or # times Milked
17. Timing of cord clamping
18. Breathing/Crying before cord clamped
19. 1 and 5 min Apgar
20. Resuscitation interventions (cpap, ppv, intubation, compressions, epinephrine, max Fio2)
21. NIRS, HR, SpO2 in del room
22. Gestational Age
23. Birth Weight
24. Gender
25. Disposition(NICU, Death or Dyad care)
26. Infant/delivery risk factors
27. NICU admission Dx
28. Reason Peds called to delivery
29. Multiple Gestation
30. COVID-19 confirmed positive

Infant data collected after consent:

31. Length, FOC (cm)
32. SGA (<10%)
33. Race/Ethnicity
34. Cord Gasses (ven/art)
35. Baby blood gas- First available
36. Hypoglycemia- First 24 hrs
37. Volume Bolus (i.e. NS) First 24 hrs
38. Hemoglobin 12-48 Hrs of life
39. Measures of cardiac function
40. Peak total bilirubin (serum or transcutaneous, Bhutani nomogram)
41. Duration of phototherapy days
42. Polycythemia within 1st week
43. PPHN
44. Therapeutic Hypothermia
45. Seizures (Confirmed by neurologist)
46. HIE: Mild, Mod, Severe (initial screen completed 1-6 hours)
47. HIE: Mild, Mod, Severe (highest stage before discharge)
48. MRI white matter injury
49. NICU admission BP
50. Use of cardiac inotropes (dopamine, dobutamine, epinephrine)
51. Early onset sepsis (positive blood or CSF culture at \leq 72 HOL) (yes/no)
52. Duration of intubated and mechanical ventilation (days)
53. Need for Blood Transfusion (DOL of 1st transfusion and total number)
54. Need for other blood products (PLT, FFP, Cryo)
55. Placental Pathology
56. Length of hospitalization (total days)
57. Concurrent study enrollment
58. Severe IVH (Grade 3-4)

**Developmental screening through 2
years of age**

59. Medical history at 3 and 18 months
60. ASQ- at 6, 12 and 24 months
61. MCHAT Survey at 24 months
62. BSID III at 2 years of age if done
63. COVID-19 confirmed positive

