Each site PI (perinatal provider and neonatologist) will orient their colleagues, delivery room and operating room staff to the study and its protocols. The site PIs will train their providers and staff to ensure that the cord is milked in a standard manner (if in the cord milking epoch), and record time elapsed from delivery until the clamping and cutting of the umbilical cord (both UCM and ECC epoch).

Protocol for the Control and Intervention Procedures

UCM: The delivering practitioner will place the newborn below the level of the incision (at the edge of the table) at C/S and a second team member will milk the cord four times. For vaginal delivery, the delivering obstetrician, midwife or perinatal provider will hold the infant against their body or place the infant on the mother's abdomen and the cord will be milked either four times by the obstetrical provider or by a second team member. For the cord milking procedure, the obstetrical provider will milk the entire length of umbilical cord over two seconds, repeating three additional times as described previously. This time is not significantly different from the time for ECC as we have demonstrated in our previous trials.

ECC: This will occur by clamping the umbilical cord as soon as possible. Since both ECC and UCM will occur after a brief assessment, it is important to note that the cord clamping time will be longer than in previously conducted preterm trials (average 20 seconds) which performed the intervention on all subjects regardless of whether or not they were vigorous. In all cases, the cord clamping time will be documented to ensure consistency.

Protocol Deviations include: a) patient did not receive correct treatment arm, b) cord clamping time of ≥ 60 seconds.

IV. SPECIFIC AIMS AND HYPOTHESES

Specific Aim 1 (PRIMARY OUTCOME) Compare the incidence of admission to the NICU in 35-41+6 week gestation non-vigorous newborns receiving UCM to those receiving ECC.

H1: Compared to ECC subjects, UCM subjects will have a decreased incidence of NICU admission.

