At the three sub-study sites, the use of NIRS is standard of care and therefore will be collected along with other data as part of the minimal data set. As part of the NIRS sub-study, sites will collect physiological and resuscitation data from birth (mean airway pressure, fractional oxygen) in addition to cerebral oxygenation. Once the newborn is delivered, receives the intervention (UCM or ECC), and is stabilized during resuscitation, a NIRS sensor (Fore-Sight, CAS Medical, Branford, CT) will be placed on the right forehead within 10 minutes of life. While arterial saturation and heart rate data will be available to the clinical team, data from NIRS will be blinded. Data on all study infants will be recorded for the first 10 minutes in the delivery room at the three sites. Heart rate, oxygen saturations, and cerebral oxygenation will be downloaded as per site's practice for neonatal resuscitation. If an enrolled infant has recovered and is stable enough for maternal bonding, NIRS may be discontinued prior to 10 minutes of life and will not be a protocol deviation.

H3: UCM subjects will receive a greater placental transfusion as estimated by hemoglobin levels by 48 hours of life and better blood pressure; UCM subjects will not have increased rates of hyperbilirubinemia compared to ECC subjects; UCM subjects will have decreased incidence and severity of HIE, decreased resuscitation interventions, decreased use of therapeutic hypothermia and use of volume expanders, and a shorter length of hospitalization.

Rationale: These variables are chosen to assess the efficacy (hemoglobin) as well as safety (bilirubin) of both cord interventions. Data will be collected from the subject's chart.

H4: UCM subjects will have improved developmental scores on the Ages & Stages Questionnaire at 2 years of age and UCM subjects will have a lower rate of medium to high-risk scores on the MCHAT at 2 years of age.

Neurodevelopmental Follow-up Strategy

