All infants that qualify for additional neurodevelopmental assessments (i.e. abnormal cord gases and/or receipt of therapeutic hypothermia) will also have their 2 year Bayley Scores collected when available. This subgroup will inform us as to whether UCM attenuates or improves long-term outcomes in infants with HIE.

Expectations, Limitations & Alternatives of Neurodevelopmental Follow-up

Each site will include a designated neurodevelopmental follow-up team responsible for maintaining periodic contact with the child's family, facilitating completion of ASQ-3 at 6, 12 and 24 months and MCHAT-R at 24 months, questionnaires scoring, data collection and entry. The follow-up team will also provide feedback to the family concerning developmental screening results and will refer children to appropriate resources whenever significant problems are identified. To enhance the follow up rate, a tracking system will be developed at each study site in which the neurodevelopmental follow-up team, or research coordinator, will maintain ongoing contact by text, phone, e-mail and/or written communication (letter, greeting cards, etc) with the family during initial hospitalization and at 3, 6, 9, 12, 18, and 24 months. Our goal is 90% follow-up.

Procedures

At Participant Enrollment

The coordinator at each site who consents the parents at the time of enrollment, will explain the need for follow-up, and describes the process we will use.

3 and 18 Month Follow-Up

The Follow-Up coordinator will contact the parent by phone. After appropriate greetings and general inquiry about the mother's wellbeing, s/he will ask about the infant's wellbeing, feeding methods, hospitalizations, health problems, or any follow-up with specialists. This information will be captured in Redcap. Any change of address or name should be requested and noted and the parent or caretaker should be reminded of the upcoming ASQ-3.

6, 12 and 24 Month Follow-Up

Approximately 1 month before the infant reaches each ASQ-3 milestone, the research team member will contact the parent by phone to discuss the upcoming ASQ-3 completion. This will include obtaining the parents preference of administration

(computer, paper copy, phone completion with assistance). The same health information will be solicited and contact information will be confirmed. Study personnel will contact the parent if the form is not returned within 1 month and will assist in completing over the phone.

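### Blood pressure is recorded only at NICU admission, and the 2-year Bayley subgroup is entered partly through therapeutic hypothermia; if UCM reduces those events, as the plan expects, the measured infants are not comparable between arms

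*Combined protocol and SAP*

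**What the plan says.** **Blood pressure.** H3 in Section IV states: "UCM subjects will receive a greater placental transfusion as estimated by hemoglobin levels by 48 hours of life and better blood pressure". The Protocol Summary carries the same hypothesis. Neither limits it to admitted infants. Appendix 1, in the list of infant data collected after consent, has one blood pressure item: "49. NICU admission BP".

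**The selecting event.** The primary hypothesis in Section IV is "H1: Compared to ECC subjects, UCM subjects will have a decreased incidence of NICU admission", and the sample size in Section V assumes "a clinically meaningful 35% reduction in NICU admissions (16.25% for UCM versus 25% for ECC".

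**Bayley subgroup.** Under the neurodevelopmental follow-up strategy in Section IV, 2-year Bayley scores are gathered, where they exist, for infants who "qualify for additional neurodevelopmental assessments (i.e. abnormal cord gases and/or receipt of therapeutic hypothermia"). The purpose follows directly: "This subgroup will inform us as to whether UCM attenuates or improves long-term outcomes in infants with HIE". H3 expects UCM to lower the incidence and severity of HIE and the use of therapeutic hypothermia.

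**Status.** Section V, Exploratory Analyses: "Several outcomes are identified as exploratory (level of HIE, blood pressure, length of hospitalization, resuscitation interventions, and placental pathology"). These outcomes are to be summarised rather than tested. The next paragraph sends all secondary and exploratory outcomes of the delivery hospitalization to the primary paper. Bayley is not a listed endpoint and has no analysis method in Section V.

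**The concern.** Randomization makes the arms comparable as enrolled. It does not make a subset comparable when treatment helps decide who enters it. NICU admission and therapeutic hypothermia both happen after cord management, and the plan predicts that UCM makes both less frequent. If that is true, the UCM infants who are still admitted, or still cooled, are not the counterparts of the ECC infants who are. When the milder cases are the ones kept out of the subset, the remaining UCM infants are on average sicker at the outset.

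Two stated aims are at stake: the blood pressure part of H3, and the follow-up section's question about UCM in infants with HIE. UCM could succeed on the primary outcome and still look neutral or slightly worse on these two measures, with nothing in the plan to tell the reader why.

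**Working it through.** **1. Is there another source of blood pressure?** I checked each place where data are defined.
- Appendix 1: item 49 only.
- Section IX, Data Collection, the waiver set and the full set after consent: no blood pressure.
- Appendix 3, delivery room form: none.
- Echo sub-study: superior vena cava flow and right and left ventricular output, no blood pressure.

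Item 49 is therefore the only source.

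**2. The plan's own figure.** No sample size or power is given for blood pressure or Bayley. The 1200 for the primary outcome, which supplies the admission rates used below, does reproduce:
- 25% against 16.25%, two-sided 0.05, 85% power: 383 per arm.
- Design factor 1 + (m − 1) × 0.02 − m × 0.02 = 0.98, so 2 × 383 × 0.98 = 751.
- Small-cluster correction 4 × 120 = 480, with 120 = 1200/10. Total 751 + 480 = 1231, within 3% of 1200.

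**3. How many infants would have a blood pressure value?** Assumption: physical admission runs at the planned endpoint rates.
- ECC: 600 × 0.25 = 150.
- UCM: 600 × 0.1625 = 97.5.
- Together 247.5 of 1200 = 20.6%, before loss from non-consent.

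**4. Size of the distortion when UCM has no effect on blood pressure.** Assumptions: one standard normal severity scale; infants above a threshold are admitted; the lower UCM rate arises because the least severe admissions no longer occur. Mean severity among those admitted is φ(z)/p.

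| Arm | p | z | mean severity |
|---|---|---|---|
| ECC | 0.25 | 0.674 | 1.271 |
| UCM | 0.1625 | 0.984 | 1.513 |

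Imbalance: 1.513 − 1.271 = 0.241 SD on unrounded values. The spurious blood pressure difference (UCM − ECC) is −r × 0.241, where r is the assumed strength of the link between severity and low blood pressure:

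| r | difference, SD |
|---|---|
| 0.1 | −0.02 |
| 0.3 | −0.07 |
| 0.5 | −0.12 |
| 0.7 | −0.17 |

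**5. Direction under a different mechanism.** Suppose instead that UCM lowers severity in every infant. The two rates then imply a shift of 0.984 − 0.674 = 0.310 SD. Admitted UCM infants average 1.513 − 0.310 = 1.203 against 1.271, so a difference of 0.068 SD in UCM's favour remains. Here selection pulls a real benefit toward zero rather than reversing it. These figures describe severity, not blood pressure.

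**6. Bayley.** The entry rule has two sufficient routes. Abnormal cord gas reflects condition at birth and is not something the plan says UCM will reduce. Hypothermia is. The documents give no rate for either route and no overlap between them, so the net bias in the combined subgroup cannot be computed. What can be said is that the hypothermia route, and the reading restricted to infants with HIE, both condition on events that H3 expects UCM to change.

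**The case against.** The case against acting is substantial, and much of it stands.

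- **Both analyses are already limited.** Blood pressure is exploratory and untested, and Section V confines other treatment comparisons in subgroups to generating hypotheses. The planned 24-month comparison is ASQ-3 and M-CHAT-R in all followed infants. This lowers the stakes, but a descriptive mean by arm carries the same selection as a tested one. The plan takes exploratory hospital outcomes into the primary paper without saying that blood pressure applies to admitted infants only.
- **The bias is small against the noise.** With 150 and 97.5 infants, the simple standard error is √(1/150 + 1/97.5) = 0.13 SD, ignoring clustering. Up to r = 0.5 the spurious difference is below one standard error; at 0.7 it is about 1.3. That stands.
- **One severity scale is a simplification.** Appendix 2 admits infants for reasons as different as hyperbilirubinemia, hypoglycemia and temperature instability. That stands, and argues for the lower part of the range.

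A reader might also infer four stronger things that the documents do not support:

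- *That blood pressure exists only for infants with the primary event.* Appendix 2 does not count some admissions, such as those for a raised white cell count alone or an isolated abnormal cord gas. Such infants can have an admission blood pressure without meeting the endpoint.
- *That the Bayley subgroup is selected only by hypothermia or NICU admission.* Abnormal cord gas is sufficient by itself, and NICU admission is not a Bayley criterion.
- *That most of UCM's blood pressure benefit must vanish.* The 0.068 of 0.310 SD left in step 5 concerns latent severity and would transfer to blood pressure only if the two were perfectly correlated.
- *That both comparisons are biased as a matter of fact.* Bias requires that UCM changes the selecting event and that severity is related to the measured outcome.

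**Conclusion.** The point holds in a conditional and limited form. The only blood pressure data, and the hypothermia route into the Bayley subgroup, depend on post-randomization events that the plan expects UCM to reduce. If UCM does reduce them, these comparisons cannot support the blood pressure part of H3 or the statement about UCM in infants with HIE. The likely error is against UCM or toward no difference.

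The 0.02 to 0.17 SD for blood pressure rests on three assumptions: physical admission near the planned rates, the threshold model, and a correlation between 0.1 and 0.7. None of these can be checked from the documents. For Bayley the point rests on the selection rule alone and has no size. The consequence is confined to what the trial may conclude on these two items.

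**What to change.** 1. **Blood pressure.** Reword item 49 to the first charted blood pressure and its time, in any unit, for all consented infants, and base the H3 comparison on that. If too few non-admitted infants have a charted value, report blood pressure as applying to NICU-admitted infants and not comparable between arms, and do not use it as evidence for H3.
2. **Bayley.** Base any between-arm comparison on the abnormal cord-gas criterion (item 34, already collected). List infants who qualify only through hypothermia descriptively. Replace the sentence about HIE with one saying that the hypothermia/HIE subgroup is descriptive and does not estimate the effect of UCM.

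**Cost.** One reworded chart field and a few sentences, with no new procedure. Blood pressure will be missing for some well infants, since the documents do not say that it is charted in dyad care. The Bayley set becomes smaller. Cord gases are recorded only if available, and the documents do not say whether they are sampled before or after milking. Bayley scores would still be collected only where they exist, so that selection remains and should be stated.
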